## Study Overview

A cluster randomized controlled trial of 18 school based health centers (SBHCs) with 1,360 Latina adolescents evaluated the extent to which the app: (1) supports adolescents in making decisions about an effective method of contraception; (2) improves the effectiveness and efficiency of the clinical encounter; and (3) reduces the incidence of unprotected sexual intercourse among Latina adolescent girls over time. The long term goal of the intervention is to reduce health disparities in unintended pregnancy rates for Latina adolescents. Clinics provided all adolescent girls with an iPad. The iPad assessed eligibility and obtained consent. Participants in the nine intervention clinics received the app and those from nine control clinics received standard of care sexual health questions. In addition to the baseline, pre-visit questionnaire, participants were asked to complete follow-up surveys within 48-hours, 3 and 6 months after the visit. Differences in adolescents' contraceptive knowledge, attitudes, self-efficacy and use over the 6-month follow up was assessed by generalized mixed effects models that to account for repeated measures, a time effect, the time by group interaction, and demographic covariates.

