#### Exclusion criteria

Adolescents were not eligible to participate in the study if they were:

- Not biologically female
- 13 years or younger or 19 years or older
- Did not identify as Hispanic/ Latina
- Used the app outside of a participating SBHC appointment
- Not sexually active
- Pregnant at the time of screening
- Using a LARC method of contraception at the time of screening
- Did not complete the intervention or baseline questionnaire

SBHCs were randomly assigned, at equal chance, to either the intervention (*Health-E You/Salud iTu* app) or control group (standard of care, no app). This design allows our analyses to isolate the effect of the app and determine whether the app increases adolescent sexual health and contraceptive knowledge, self-efficacy in selecting an effective method, satisfaction with the visit and contraceptive use and adherence over time.

Clinics were randomized to either control or intervention group using computer-generated random number assignment. Following randomization, our local partners from The Los Angeles Trust for Children’s Health (LA Trust) notified the SBHCs of their assignment and provided the necessary training around the study aims, use of the iPad and integration into the unique workflow at each SBHC (determined in partnership with our community outreach staff and clinic staff, providers and managers). The LA Trust also provided technical support to ensure that all sites had a reliable internet connection to be able to use the app as intended and to securely transmit data gathered from the app to the University of California, San Francisco (UCSF).

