#### Study Outcomes

The outcomes for this study were developed in collaboration with our community, clinic and adolescent partners to address three main questions:

- 1) How well does the patient-centered, interactive, individually tailored *Health-E You* app engage and support Latina adolescents in understanding their risk of an unintended pregnancy and in making decisions in selecting among effective contraceptive options that can reduce their risk?
- 2) To what extent does the app improve adolescents' and clinicians' perception of the quality and efficiency of the visit?
- 3) How well does the app improve, sexually active Latina adolescents use of and adherence to effective contraceptives over time?

From these questions, we developed the specific study aims and corresponding outcome measures. The following is a description of each outcome measure for each study aim, the type of outcome (primary or secondary), the rationale for the outcome measure and the purpose for the measure.

**Aim 1: Examine the extent to which the Health-E You contraceptive app supports adolescents in making decisions about an effective method of contraception.**

Aim 1a) increase adolescents' knowledge of sexual health and contraceptive options

Outcome Measure: Knowledge was a secondary measure that was assessed with a 7-item scale that used a true/false format (scores range 0-7). A higher score indicates more knowledge. The items are: 1) Birth control pills do not reduce the risk of getting a sexually transmitted disease (STD); 2) As long as the male partner pulls out before he ejaculates (cums), the female will not get pregnant; 3) Weight gain is a common side effect of most birth control methods, especially for the Intra-Uterine Device (IUD); 4) Birth control pills begin working as soon as you start taking them; 5) Decreased menstrual bleeding from using IUDs does not cause health problems later on; 6) Long-acting contraception methods, like the IUD and implant, can make it more difficult to become pregnant in the future; 7) The IUD is easy for a medical provider to insert and remove.

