Rationale: Knowledge is an important component of the theoretical framework of the intervention aimed to change behavior. Youth indicated that misconceptions about contraception contributed to their selecting less effective methods. Youth informed content of app and corresponding knowledge items to improve the ability of the app to address common contraception misconceptions and empower youth to be more informed about their options.

Purpose: Information provided on the app was designed to increase knowledge in these key areas via a repeated, self-administered survey immediately before and again after using the app.

Aim 1b) increase the proportion of adolescents who report being prepared to select an effective form of contraception; and

Outcome Measures: Patient Activation/Readiness was measured with the following items: “The App helped me choose a method of birth control” and “The App gave me useful information about birth control”. Likert scale (options 1= strongly disagree to 5=strongly agree) which was then dichotomized into agrees versus neutral/disagrees.

Rationale: The app was designed to support adolescents in selecting a method that was a “good fit” based on their attitudes, goals, experiences and lifestyle considerations.

Purpose: To examine adolescent’s perspective on the value of the app in helping them become educated about birth control and support them in choosing a contraceptive method.

Aim 1c) increase adolescents’ self-efficacy to select and use an effective contraceptive method.

Outcome Measure: Contraception Use Self-efficacy. This primary outcome measure was based on a 3-item attitudinal scale to assess perceived confidence to choose and use contraception was self-administered via online survey. Each item scored on a 0-10 scale (0=not at all confident to 10=completely confident scale). Scale score is the sum of 3 items (range 0 – 30); higher score= greater self-efficacy. The questions were “How confident are you that you”.... 1) “can talk to your doctor about what birth control method(s) to use?” 2) “Can use birth control correctly so you do not get pregnant?” 3) “Have the information you need to choose the most appropriate birth control method for you?” It compares change in Intervention vs controls over time from baseline to 48-hour, 3-and 6 month follow-ups. Cronbach’s alpha ranged from .74 to = .80.

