We also hypothesized that mean contraception use self-efficacy would be higher in the intervention group than the control group immediately after the clinic visit (Aim 1b, Primary Outcome 1). The same analytic approach already described was implemented to assess this hypothesis with the exception that the mixed effects linear regression model included only two time points: baseline and 48 hours after baseline (which changed the sexual activity covariate to being time invariant).

Among intervention group participants only contraception knowledge was assessed immediately prior to using the *Health-E You* app and immediately after app use. We predicted mean knowledge would increase from the pre-app assessment to the post-app assessment (Aim 1a, Secondary

Outcome 1). Once again, a mixed effects linear regression analysis was employed with two time points, the same covariates, and robust variance estimation (to account for clustering by SBHC). However, since the control group was not part of the analysis, the model did not include parameters representing treatment group or the time by treatment group interaction. In this model, the time parameter was the direct test of the intervention effect.

Finally, we hypothesized that at the clinic visit (the visit immediately following recruitment and, in the intervention condition, use of the app) a higher proportion of the intervention group, when compared to the control group, would discuss birth control with the clinician (Aim 2b, Secondary Outcome 2) and receive a non-barrier method of birth control either directly or via an appointment or referral (Aim 3a, Secondary Outcome 3). These hypotheses were tested using logistic regression models regressing the dichotomous (yes-no) outcomes on treatment group (the direct test of the intervention effect), age, purpose of visit, and whether sexually active in the prior 3 months using robust variance estimation (to account for clustering by SBHC).

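### Knowledge (Aim 1a, Secondary Outcome 1) is a one-arm pre-post change, yet the plan labels it the direct test of the intervention effect and elsewhere describes it as a randomised comparison

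*Combined protocol and SAP*

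**What the plan says.** Study Outcomes, Aim 1a, defines the measure: "Knowledge was a secondary measure that was assessed with a 7-item scale" of true/false items, scored 0 to 7. Its purpose statement says the information was gathered "via a repeated, self-administered survey immediately before and again after using the app".

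Analytical and statistical approaches gives the analysis. "Among intervention group participants only contraception knowledge was assessed immediately prior to using the" app, and again immediately after app use. The model has two time points, the common covariates and robust variance by clinic. On the control arm it says that "since the control group was not part of the analysis, the model did not include parameters representing treatment group"; an interaction term is likewise absent. It then concludes: "In this model, the time parameter was the direct test of the intervention effect".

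Two other places describe something different:

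- Study Overview: differences in "contraceptive knowledge, attitudes, self-efficacy and use over the 6-month follow up was assessed by generalized mixed effects models" that include a time-by-group interaction.
- The randomisation text under Exclusion criteria: "This design allows our analyses to isolate the effect of the app and determine whether the app increases adolescent sexual health and contraceptive knowledge".

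Aim 1b is worded as an aim to "increase the proportion of adolescents who report being prepared to select an effective form of contraception". The two items listed for it both ask about the app. Aim 2a is worded as improving perceptions of the visit; its eight adolescent items and four provider opinion items concern the app, and three provider time items do not mention it.

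**The concern.** The same description, a direct test of the intervention effect, is attached to the randomised contrasts (the time-by-group interactions for self-efficacy and contraceptive use, and the treatment term in the logistic models) and to a one-arm time coefficient. A reader cannot tell from the label which results are protected by randomisation.

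For knowledge there is no such protection. The girls answer the same true/false items before and after the app. Scores may rise because the app taught them something, because the first round of questions cued attention to the answers, because answering twice helps by itself, or because recall is tested straight after exposure. No group without the app is in the model to show how much of the change would have occurred anyway.

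What is at stake is one secondary claim, which the Study Overview and the randomisation text present as a result of the randomised design.

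**Working it through.** **1. The three statements side by side.**

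| Place | Arms | Time span | Test |
|---|---|---|---|
| Study Overview | Group comparison implied | 6-month follow-up | Time-by-group interaction |
| Randomisation text (under Exclusion criteria) | Both, by design | Not stated | Design said to isolate the app's effect |
| Analytical and statistical approaches | Intervention only | Immediately before to immediately after app use | Time parameter, no group term |

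The third is the only operational description, and the purpose statement for Aim 1a agrees with it. The other two cannot both stand beside it.

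**2. What the time parameter estimates.** In one arm,

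time parameter = app effect + (re-test + cueing + immediate-recall effects).

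Only the sum is identified. Had both arms been measured twice, the interaction would be the difference between arms in change, and a re-test gain common to both arms would cancel.

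**3. Illustrative size.** Table 1 covers contraceptive receipt and use only, so there is no knowledge figure to reproduce. Its method can be checked and borrowed. For the visit row (N = 505, 18 clinics, ICC .01), the design effect is 1 + (505/18 − 1) × .01 = 1.271 and the effective n per arm is 252.5/1.271 = 198.7. Then h = (1.96 + 0.8416) × √(2/198.7) = 0.281, against the printed .282.

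Inputs from the documents: 1,360 participants, 9 clinics per arm, alpha .05 (taken as two-sided), power .80, ICC .01/.05/.09 from Table 1. Assumed: 680 girls in the intervention arm (1,360/2), an SD of change of 1 to 2 points, and that Table 1's ICC range applies to change in knowledge.

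Design effect = 1 + (680/9 − 1) × ICC = 1.75, 4.73 and 7.71 at ICC .01, .05 and .09. SE = SD × √(design effect/680). The smallest significant mean gain is 1.96 × SE:

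| SD of change | ICC .01 | ICC .05 | ICC .09 |
|---|---|---|---|
| 1.0 | 0.10 | 0.16 | 0.21 |
| 1.5 | 0.15 | 0.25 | 0.31 |
| 2.0 | 0.20 | 0.33 | 0.42 |

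The range is 0.10 to 0.42 points, or 1.4% to 6% of the 7-point scale. With a t reference on 8 df (9 clinics) it is 0.12 to 0.49. These are significance thresholds: a true gain of exactly that size would be detected only about half the time.

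**4. If the app did nothing.** Suppose re-answering alone raised the mean by 0.3 points (an assumption). With an SD of change of 1.5, the SEs are 0.076, 0.125 and 0.160, and the probability of p<.05 is 0.98, 0.67 and 0.47 at ICC .01, .05 and .09. Over SDs of 1 to 2 it runs from 0.29 to 1.00.

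**5. For comparison.** A two-arm time-by-group test on the same assumptions would detect a difference in change of 0.20 to 0.84 points at 80% power (2.8016 × SD × √(2 × design effect/680)), or 0.21 to 0.90 with a t reference on 16 df.

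**The case against.** The plan is open about the one-arm analysis: it says in terms that controls were not in the model, and the hypothesis is stated as a rise from the pre-app to the post-app assessment. Knowledge is secondary. Self-efficacy, contraceptive use, discussion of birth control and receipt of a method are all compared between arms. A short interval also limits history and maturation as rival explanations. All of this stands, and it keeps the point modest. It does not remove re-test, cueing or recall effects, and disclosure in the analysis section does not correct the Study Overview or the randomisation text.

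Four stronger readings are tempting, and the documents do not support them:

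- *A positive knowledge result is a foregone conclusion.* No SD, re-test gain or ICC for knowledge is given, and the 0.29 to 1.00 range above shows how far the answer depends on assumptions.
- *The two assessments are only minutes apart.* The text says immediately before and after; it gives no duration.
- *The knowledge result will be presented as lasting to 6 months.* Only one compressed sentence in the Study Overview points that way; the stated hypothesis is immediate.
- *Aims 1b and 2a as a whole cannot show an effect.* The three provider time items do not mention the app, and the documents do not say which arm answered them. The analysis section attaches the label Aim 1b to a randomised 48-hour comparison of self-efficacy, although Study Outcomes places self-efficacy under Aim 1c. The purpose and rationale texts already treat the app-worded items largely as user ratings, and no test of them is planned.

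**Conclusion.** Wrong as written for knowledge. The time parameter tests pre-post change among app users; it does not isolate an intervention effect by randomised comparison, and the Study Overview and randomisation text claim a property that the analysis lacks. This conclusion is structural and needs no assumed figure. The 0.10 to 0.42 point threshold illustrates only that a small uncontrolled gain could reach significance, and it rests on the assumed arm size, SD of change and ICC, with a normal reference.

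A minor note goes with it. The two app-worded Aim 1b items and the app-worded Aim 2a items have no stated baseline and no stated between-arm comparison, so they describe ratings and cannot support a conclusion that something increased or improved. The three provider time items are outside this point. No primary outcome is touched.

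**What to change.** For knowledge:

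- Rename Secondary Outcome 1 *immediate within-arm pre-post change in knowledge among app users*.
- In Analytical and statistical approaches, describe the time parameter for this outcome as a *test of pre-post change*.
- Take knowledge out of the Study Overview sentence on 6-month models, and out of the randomisation text's claim about what the design isolates.

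As a minor item:

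- Report the app-worded Aim 1b and Aim 2a items as proportions agreeing among respondents who used the app, or providers rating it, with cluster-adjusted intervals and no conclusion of increase or improvement.
- Reconcile the Aim 1b label on the 48-hour self-efficacy comparison with its placement under Aim 1c in Study Outcomes.

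The cost is wording and interpretation, plus intervals for a few proportions. No new data are needed, and one secondary claim is narrowed.

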**Aim 3: Evaluate the effectiveness of the Health-E You contraceptive app to reduce the incidence of unprotected sexual intercourse (and associated unintended pregnancies) among Latina adolescent girls.**

3a) increase the proportion of sexually active adolescents who receive an effective contraceptive at their clinic visit

Outcome Measure: The primary outcome is the proportion of adolescent participants who report receipt of a non-barrier contraceptive method at their visit, a prescription for contraception or a follow-up appointment/referral for contraception. This was assessed at the 48-hour follow-up survey for both intervention and controls. Participants responded to the query of “Which of the following happened at this visit” (recent visit with your health care provider in which you used the Health-E You App via a self-administered survey at the 48-hour follow up): 1) Received birth control; 2) Made an appointment to receive contraception in the future; 3) Received prescription of hormonal contraception; 4) Did not receive a birth control prescription, referral or actual method.

Rationale: Receipt of effective non-barrier contraceptive methods is a central component reflecting the efficacy of the App to improve effective contraceptive use in this population. This measure helps to identify what happened during the health care visit, and to see if the Health-E You App improved the youth’s receipt of contraceptive services during their clinical visit.

Purpose: To assess the effectiveness of the app in improving the proportion of adolescents who receive contraception at their visit where they used the app.

3b) increase the proportion of sexually active adolescents who adhere to an effective contraceptive method over time -- at three and six months after their clinic visit.

Outcome Measure: This primary outcome measure was: self-reported use of non-barrier contraception in the prior 3 Months (along with type of contraceptive) assessed at baseline, 48 hour, 3- and 6 month follow-ups. Contraceptive methods were

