### Sample Size Calculations and Power

In designing this study, we adhered to the criteria of the PCORI methodology principals that pertain to the development of research questions.iii We used preliminary studies to estimate that approximately 80% of the eligible adolescents would agree to participate. The goal was to enroll a total sample of **1400** sexually active Latina girls aged 14-18 in the study (700 per treatment group). Sample size estimates and power analyses were based on a 40% attrition rate by the 3-month follow up (**840** total, 420 per treatment group) and another 10% by the 6-month follow-up (**700** total, 350 per treatment group).

Assuming power = .80 and alpha = .05, the minimum detectable difference in the primary behavioral outcome at each time point between the intervention and the control condition is 12-14, 18-19 or 22-23 percentage points depending on whether the intraclass correlation (ICC) assessing the

clustering effect of clinics is low, moderate, or high. Prevalence of outcomes in the control condition come from the final data set after completion of data collection, and the ICC range is suggested by data from Reading et al.iv The calculated differences in proportions translate into an effect size (Cohen’s h) falling between a small (h=.20) and medium (h=.50) effect size for all three levels of ICC. Specifically, regarding evaluation of the intervention condition, the minimum achievable precision for point estimates of proportions is a confidence interval width of 11 percentage points for visit data, and 12 percentage points for 3-month data and 6-month data.

The calculated differences in proportions translate into an effect size (Cohen’s h) falling between a small (h=.20) and medium (h=.50) effect size for all three levels of ICC. Specifically, regarding evaluation of the intervention condition, the minimum achievable precision for point estimates of proportions is a confidence interval width of 11 percentage points for visit data, and 12 percentage points for 3-month data 6-month data.

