**Table 1: Power Analysis**

Outcome	Minimum detectable change if:				
	% of Baseline Sample (N)	Control Proportion	ICC=.01 Change (h)	ICC=.05 Change (h)	ICC=.09 Change (h)
Receive effective method at visit*	37% (505)	39%	+14% (.282)	+19% (.380)	+23% (.456)
Use effective method at 3 months	45% (616)	45%	+13% (.26)	+18% (.365)	+22% (.445)
Use effective method at 6 months	49% (669)	33%	+12% (.255)	+18% (.361)	+22% (.441)

\* Analysis is limited to participants not already using an effective contraceptive method.

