#### Handling Missing Data

Since each assessment involves a relatively brief self-administered instrument, the amount of missing data due to failure to provide data was minimal. The largest source of missing data was participant dropout. Of the 1360 participants in the study cohort 778 (57.2%) responded to the 48-hour survey, 681 (50.1%) responded to the 3-month survey, 676 (49.7%) responded to the 6-month survey, and 575 (42.3%) responded to both the 3-month survey and the 6-month survey.

Consequently, to minimize bias due to attrition, we employed multiple imputation so that every regression model could be fit to all available data while invoking the mild assumption that the data were missing at random. Imputation was performed on the data in wide format (one record per case) to correctly account for dependence in multiple observations per case. In models testing a time by treatment group, missing data were imputed separately for intervention cases and control cases. Imputation models contained all variables in the analysis model (including the outcome), baseline variables identified as correlates of retention, and indicator variables representing recruitment site (SBHC).

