#### Heterogeneity of Treatment Effects

A concern in any cluster randomized control trial is whether or not the treatment effect is robust across sites. However, small per site sample sizes preclude direct comparisons between sites because of a lack of statistical power. We investigated the sensitivity of the intervention effect to recruitment site (SBHC) in the two primary outcomes where we assessed changes from baseline to

3-month and 6-month follow-up: contraception use self-efficacy (Aim 1c, Primary Outcome 2) and non-barrier contraception use (Aim 3b, Primary Outcome 3). For both outcomes, the time by treatment group interaction served as the direct test of the intervention effect. With three time points and two treatment groups, the interaction was represented by two parameter estimates. The sensitivity analysis employed a jack-knife technique where the analysis is repeated but with participants from one intervention SBHC removed from the analysis. Since there were 9 SBHCs randomly assigned to each treatment group, the jack-knife technique required 9 new models be assessed.

Table 2 reports the point estimate, 95% confidence interval, and p-value for each parameter obtained from the mixed effects regression analysis model including all 9 intervention SBHCs plus the range of parameter estimates and p-values obtained from the jack-knife analyses (models that included only 8 intervention SBHCs).

**Table 2. Parameter Estimates from Sensitivity Analyses Compared to Parameter Estimates from Analytic Models for Two Primary Outcomes**

Outcome	Interaction Parameter	Estimate	Analytic Model		Sensitivity Analyses	
			95% CI	p-value	Estimates	p-value
Contraception Use Self-efficacy	1	0.816	-0.482, 2.115	.218	0.477-1.086	.098-.408
	2	1.576	0.377, 2.774	.010	1.269-1.729	.006-.037
Non-barrier Contraception	1	1.190	0.043, 2.338	.042	1.128-1.350	.024-.063
	2	1.711	0.529, 2.544	.005	1.511-1.936	.003-.012

For both outcomes, the data suggest the intervention effect is not sensitive to recruitment site (SBHC).

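### The Aim 2b visit model omits baseline non-barrier use, which was collected, and Table 1 restricts the Aim 3a population while the methods text does not

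*Combined protocol and SAP*

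**What the plan says.** The combined protocol and SAP, under Analytical and statistical approaches, gives one specification for both visit outcomes: discussing birth control (Aim 2b, Secondary Outcome 2) and receiving a non-barrier method (Aim 3a, Secondary Outcome 3). It reads "These hypotheses were tested using logistic regression models regressing the dichotomous (yes-no) outcomes on treatment group (the direct test of the intervention effect), age", followed by "purpose of visit, and whether sexually active in the prior 3 months using robust variance estimation (to account for clustering by SBHC". No baseline contraceptive variable appears, and no subset of participants is named.

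Other sections bear on this:

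- **Study Outcomes, Aim 3b** lists "self-reported use of non-barrier contraception in the prior 3 Months (along with type of contraceptive) assessed at baseline", so the variable is on file.
- **Exclusion criteria** remove girls who did not complete the baseline questionnaire. Near-complete baseline data are therefore a fair inference, though not stated item by item.
- **Inclusion criteria** bar only users of long-acting methods, so users of the pill, patch, ring or shot are in the cohort.
- **Table 1**, in a footnote attached to the visit-receipt row alone, says "Analysis is limited to participants not already using an effective contraceptive method". That row has N=505.
- **Handling Missing Data** says multiple imputation was used so that "every regression model could be fit to all available data". The imputation models hold the analysis-model variables, baseline correlates of retention, and site indicators.

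**The concern.** Whether a girl already uses a non-barrier method plausibly predicts whether birth control is discussed at her visit. The longitudinal outcomes carry their own baseline value through the time-by-group interaction. The visit outcomes have no baseline measurement of their own, so a related baseline variable is the natural substitute, and the model leaves it out.

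With 18 clinics randomised and no stratification described, the share of users could differ between arms by chance. That difference would pass into the Aim 2b comparison. The omission may also reach the imputation. Of 1360 girls, 1360 − 778 = 582 (43%) lack the 48-hour survey, and baseline use enters the imputation model only if it is in the analysis model or happened to correlate with retention.

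For Aim 3a the issue is different. One part of the document restricts the analysis to non-users and another does not, so the reader cannot be sure which girls the estimate describes. Candidate denominators are 505, the 778 respondents, all 1360 after imputation, or the imputed non-users (about 1360 × 505/778 = 883, if the share holds). Study Outcomes calls receipt a primary outcome while the methods text calls it secondary, so its population should not be left to inference.

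**Working it through.** **1. Reproduce the Table 1 visit row.** Inputs: N=505, control proportion 39% and ICC .01/.05/.09 (Table 1); "Assuming power = .80 and alpha = .05" (two-sided assumed); 18 clinics, "Since there were 9 SBHCs randomly assigned to each treatment group".

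- Design effect = 1 + (505/18 − 1) × ICC = 1.271 / 2.353 / 3.435.
- h = (1.960 + 0.842) × √(2 × design effect / 252.5) = .281 / .382 / .462. Table 1 has .282 / .380 / .456.
- Back-transformed from 39%: 14.0 / 19.0 / 22.9 points. Table 1 has 14 / 19 / 23.

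The row reproduces on 505 girls. That is fewer than the number who answered at 48 hours ("Of the 1360 participants in the study cohort 778 (57.2%) responded to the 48-hour survey"), which fits the footnote's restriction.

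**2. Aim 2b: how large could chance imbalance be?** The documents give no baseline use by arm, so two assumptions are needed:

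- the 505 are the non-users among the 778 respondents, so users number 778 − 505 = 273 (35.1%);
- baseline use has the same ICCs as Table 1's outcomes.

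With 389 per arm:

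- Design effect = 1 + (778/18 − 1) × ICC = 1.42 / 3.11 / 4.80.
- SD of the difference in user share = √(2 × .351 × .649 × design effect / 389) = 4.1 / 6.0 / 7.5 points.
- 95% range = ±1.96 SD = about ±8 / 12 / 15 points.

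The first assumption can be varied. Table 1's 3-month and 6-month rows use 616 of 681 and 669 of 676 respondents, so 1% to 10% are lost there without explanation. Taking the larger loss, 778 × 616/681 = 704 and users = 704 − 505 = 199 (28%). The same formula with 352 per arm gives SDs of 4.0 / 5.8 / 7.1 and ranges of about ±8 / 11 / 14. The result barely moves.

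Shift in the Aim 2b risk difference = imbalance × gap in discussion rate between users and non-users. The gap is not given. For each 10 points of gap, one SD of imbalance moves the comparison by 0.4 / 0.6 / 0.75 points before adjustment. Purpose of visit, already in the model, may absorb part of this.

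**3. Aim 3a: what if users were kept?** This further assumes that the app has no effect on receipt among users. The effect is then multiplied by 505/778 = .649.

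| ICC | Effect in non-users | Power, 505 non-users | Effect in all 778 | Power, all 778 |
|---|---|---|---|---|
| .01 | 14 | 80.2% | 9.1 | 57–62% |
| .05 | 19 | 80.0% | 12.3 | 50–53% |
| .09 | 23 | 80.3% | 14.9 | 48–52% |

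The power ranges cover assumed receipt among control-arm users from 10% to 95%, without baseline adjustment. If the footnote governs, baseline use is constant in the sample and neither dilution by users nor imbalance in this variable arises.

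**The case against.** The strongest reply is that Aim 3a is already dealt with. The footnote speaks of the analysis, Table 1 draws its control proportions from the final data set, and the row reproduces on 505. Silence in the methods text does not cancel an explicit restriction elsewhere. This stands: what remains for Aim 3a is a population to be stated in both places.

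A reader might infer that both visit comparisons are diluted, or that the missing-data section overrides the footnote. The documents support neither reading. The remark about all available data explains why imputation was used for dropout and does not define analysis populations. The footnote was never attached to Aim 2b, so nothing was left unapplied there. Discussing birth control is also a meaningful outcome for current users, so including them does not in itself dilute an effect.

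It is also fair to say that chance imbalance is not bias, that the cluster-robust variance is meant to reflect between-clinic variation, and that a fourth covariate chosen after completion is discretionary. This stands in part. It makes the Aim 2b point one of precision and conditional comparability, and it requires the refit to be labelled post hoc. It does not remove the benefit of using a plausible predictor that is already held.

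**Conclusion.** The point holds in a limited form.

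- **Aim 2b:** the model omits a collected, plausibly prognostic baseline variable. The cost is lost precision and exposure to chance imbalance, with no systematic bias. The illustrative 95% range of imbalance is about ±8/12/15 points at ICC .01/.05/.09. It rests on the assumed user share of about 35% and on borrowing Table 1's ICCs. The effect on the estimate itself cannot be fixed from the documents.
- **Aim 3a:** Table 1 and the methods text must be reconciled. Shrinkage from 14/19/23 to about 9/12/15 points is conditional on users having been kept and on the app not affecting them. Nothing in the documents shows that such an analysis was run, and the more natural reading of Table 1 is that it was not.

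**What to change.** - **Aim 2b:** add baseline non-barrier use to the logistic model and to its imputation model.
- **Aim 3a:** state under Analytical and statistical approaches that the analysis is in girls not using a non-barrier method at baseline, as in Table 1. Fit it there, define baseline use, and give the denominator before and after imputation. If an all-participant model is shown as a sensitivity analysis, adjust it for baseline use and keep that variable in its imputation model.
- **Reporting:** label the refits post hoc and show them beside the models as specified. An odds ratio adjusted for baseline use is conditional on it and not directly comparable with the unadjusted one, so report the standardised risk difference as well.

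The cost is one covariate and one subset on data already held, plus rerunning the imputation. No new data collection is needed.
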